6. RESPONSE ASSESSMENT

Patients will undergo clinical head and neck exam and post-treatment CT scan with IV contrast 12-14 +/- 2 weeks following completion of IMRT. Note, an integrated PET/CT with contrasted diagnostic CT scan is recommended if feasible at the participating site; however, only a diagnostic CT scan is required. Rare patients may require an MRI for tumor measurements, due to allergy to iodinated contrast despite premedication. In these patients, MRI of the neck should be performed at baseline and at first response assessment.

Responses will be coded for:

- Clinical examination response, primary and nodes.
- CT response, primary and nodes (see modified RECIST criteria version 1.1, Section 6.1).

- If applicable: Integrated PET/CT response, primary and nodes (see Integrated PET/CT response criteria, Section 6.2.4). Solid Tumor Response Criteria (modified RECIST Criteria version 1.1)

6.1.1 Malignant Disease Evaluation

To assess objective response, it is necessary to estimate the overall tumor burden at baseline to which subsequent measurements will be compared. Measurable disease is defined by the presence of at least one measurable lesion.

All measurements should be recorded in metric notation by use of a ruler or calipers. The same method of assessment and the same technique should be used to characterize each identified lesion at baseline and during follow-up. All baseline evaluations should be performed as closely as possible to the beginning of treatment and never more than four weeks before registration.

The term unevaluable in reference to measurability will not be used because it does not provide additional meaning or accuracy. At baseline, the primary tumor and pathologic neck lymph nodes will be characterized as either measurable or non-measurable.

6.1.1.1 Measurable Disease

6.1.1.1.1 Primary Tumor

Lesions that can be accurately measured in at least one dimension (longest diameter to be recorded) as ≥ 20 mm (2.0 cm) with conventional techniques or as ≥ 10 mm (1.0 cm) with spiral CT scan.

6.1.1.1.2 Neck Lymph Nodes

Neck lymph nodes are considered pathologic and measurable if short axis ≥ 15 mm.

Neck lymph nodes are considered pathologic but non-measurable if short axis ≥ 10 mm but < 15 mm. Neck lymph nodes are considered non-pathologic and non-measurable if short axis < 10 mm.

6.1.1.2 Non-measurable disease

All other lesions, including small lesions [longest diameter < 20 mm (2.0 cm) with conventional techniques or < 10 mm (1.0 cm) with spiral CT scan] are truly non-measurable lesions.

Lesions considered to be truly non-measurable include the following: bone lesions, leptomeningeal disease, ascites, pleural/pericardial effusion,

inflammatory breast disease, lymphangitis cutis/pulmonis, abdominal masses that are not confirmed and followed by imaging techniques, and cystic lesions.

6.1.2 Definitions of a Response

6.1.2.1 Target Lesions

All measurable lesions, including the primary tumor, and up to a maximum of five neck lymph nodes, should be measured at baseline.

The sum of the longest diameter of the primary tumor, and the short axis diameter of target pathologic lymph nodes, will be calculated at baseline and reported as the *baseline sum diameter*.

6.1.2.1.1 Complete Response (CR)

The disappearance of the primary tumor and the resolution of pathologic neck adenopathy. For the definition of radiographic complete response in the neck, the resolution of neck lymph nodes to < 10 mm in short axis diameter with non-pathologic appearance is sufficient.

6.1.2.1.2 Partial Response (PR)

At least a 30% decrease in the sum of target lesion diameters (longest diameter of the primary tumor; short axis diameter of the target lymph nodes), taking as reference the *baseline sum diameter*.

6.1.2.1.3 Progressive Disease (PD)

At least a 20% increase in the sum of target lesion diameters (longest diameter of the primary tumor; short axis diameter of the target lymph nodes), taking as reference the *smallest sum diameter* recorded since the baseline sum diameter measurements, or the appearance of one or more new lesion(s).

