6.1.3.2 Confirmation of Response

To be assigned a status of complete or partial response, changes in tumor measurements must be confirmed by repeat assessments performed no less than four weeks after the criteria for response are first met.

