6.2.4 FDG-PET Scan

The ideal post-chemoradiotherapy response assessment method would accomplish two goals: 1) accurately detect viable residual disease amenable to surgical consolidation and 2) be prognostic for longer term clinical outcomes including PFS. Head and neck clinical examination alone has an accuracy of less than 50% for residual neck nodal disease,⁶³ while post-radiation diagnostic CT has higher sensitivity than clinical exam but unsatisfactory specificity.^{64,65} An increasing body of literature suggests that post-chemoradiotherapy positron emission tomography (PET), performed 8-12 weeks following completion of radiotherapy has improved accuracy relative to CT for classification of complete response in PULA HNSCC. The negative predictive value (NPV) for determination of residual neck disease, in particular, ranges from 92-100%.⁶⁶⁻⁶⁹ The University of Pittsburgh institutional experience indicates that serial PET/CT scans permit safe deferral of planned neck dissection following chemoradiotherapy. Moreover, a PET scan added to a diagnostic contrasted CT is superior to clinical examination or diagnostic CT alone

(utilizing RECIST criteria 1.0) with regard to correlation with PFS.⁷⁰ However, RECIST 1.0 criteria were developed primarily for response assessment in the metastatic solid tumor setting, where patients are treated with palliative systemic therapy. RECIST 1.0 criteria inadequately address the post-chemoradiotherapy setting. Specifically, a CR in accordance with RECIST 1.0 requires disappearance of all target lesions, including pathologic lymph nodes. However, non-pathologic, subcentimeter lymphadenopathy can persist after chemoradiotherapy. RECIST 1.1 now incorporates new guidelines for the measurement of nodal disease, and for determination of CR, a short axis of < 1 cm is no longer considered residual disease. The accuracy of the RECIST 1.1 criteria for assessment of residual disease or as a predictor of PFS following chemoradiotherapy for PULA HNSCC is not reported.

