To date, the majority of PET/CT literature conducted has been retrospective. The sole prospective study of PET/CT versus CT for first response assessment following chemoradiotherapy was performed at MDACC.⁶⁶ This study found that PET/CT was not superior to diagnostic CT alone for the accuracy of response assessment in unselected PULA HNSCC patients. However, in high risk patients defined as HPV-negative, non- oropharynx, and/or tobacco-exposed, PET/CT outperformed CT. The study has been criticized for lack of integration of a diagnostic contrasted CT into the PET/CT acquisition algorithm, although PET/CT results were interpreted with knowledge of a separate contrasted diagnostic CT; such integration enhances per-lesion sensitivity and specificity in head and neck cancer staging⁷¹ and is of theoretical utility in the post-treatment patient. The CT criteria used in the MDACC study to classify nodal disease were clinical and related to RECIST. However, long axis nodal measurements were utilized with the following categorization:

- Pathologic (residual disease) nodes: > 15 mm in longest diameter and/or necrotic appearance.
- Indeterminate nodes: 10-15 mm in longest diameter and non-specific CT findings.
- Non-pathologic nodes: < 10 mm in longest diameter and non-necrotic (CR).

At the University of Pittsburgh, the standard of care following definitive chemoradiotherapy for PULA HNSCC has been integrated PET/CT. Following PET/CT patients are placed into four clinical categories: Negative PET/CT (Complete Response); Probably Negative PET/CT (Low clinical concern; follow up indicated); Probably Positive PET/CT (Clinical concern; tissue sampling indicated); Positive PET/CT (Definite residual disease). This categorization has been found to correlate with clinical outcomes, specifically PFS.⁷²

Definition of CR following chemoradiotherapy therefore has two relevant, literature-based definitions which may be of clinical utility: 1) Quantitative anatomic criteria (RECIST 1.1); 2) Integrated PET/CT criteria.

Complete Response: Modified RECIST 1.1 (see section 6.1)

- Disappearance of primary tumor. Irregular contour of the tumor bed is consistent with -radiation change.
- Decrease in measurable pathologic neck lymph nodes to short axis measurement < 10 mm and non-necrotic appearance with normalization of nodal configuration. Increased enhancement may be attributable to radiation change.
- No new pathologic lesions.

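### The 20% progression rule has no minimum rise and no exception for complete responders, so one scan can meet both CR and PD, which can bias 1-year PFS downward

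*Combined protocol and SAP*

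**What the plan says.** Section 6.1.2.1.3 defines progressive disease (PD) in the target lesions as "At least a 20% increase in the sum of target lesion diameters", measured against the smallest sum since baseline, or as any new lesion. It gives no absolute minimum and no exception for a patient in CR.

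Section 6.1.2.1.1 defines CR as loss of the primary plus resolution of the neck nodes, for which "the resolution of neck lymph nodes to < 10 mm in short axis diameter with non-pathologic appearance is sufficient". Section 6.2.4 restates it as "Decrease in measurable pathologic neck lymph nodes to short axis measurement < 10 mm and non-necrotic appearance", with normal nodal configuration and no new lesions. Section 6.1.1.1.2 says "Neck lymph nodes are considered non-pathologic and non-measurable if short axis < 10 mm", and Section 6.2.4 gives the background: "non-pathologic, subcentimeter lymphadenopathy can persist after chemoradiotherapy".

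The target set is the primary and "up to a maximum of five neck lymph nodes" (Section 6.1.2.1). Confirmation is required only for response: "To be assigned a status of complete or partial response, changes in tumor measurements must be confirmed by repeat assessments" (Section 6.1.3.2). None is stated for PD.

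Section 6.1.3.7 counts disease progression in PFS without defining it separately. Section 9 makes 1-year PFS one of three criteria for advancing an arm, and the deciding measure if both arms qualify.

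**The concern.** The CR rule allows for small residual nodes after chemoradiotherapy, but the PD rule does not. After a good response the smallest sum may be only a few millimetres, so 20% of it can be 1 to 2 mm. A change that small may be reading variation rather than growth.

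The patients exposed are those with small residual nodes, that is, good responders. A false call lowers 1-year PFS. It could fail a schedule that should advance, and it adds noise to the choice between schedules.

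**Working it through.** **Plan's own figures.** The protocol gives no rate for false progression, and Figure 1 is not shown, so no acceptance probability can be reproduced. The sample size does reproduce: 40/(1 − 0.10) = 44.4, rounded up to 45 per arm, or 90 in total.

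**Overlap of CR and PD.** Take the primary as gone and one target node (or equal nodes rising together) with nadir *m*.
- PD needs a reading of at least 1.2 × *m*; the CR size limit needs a reading below 10 mm.
- Both can hold when 1.2 × *m* < 10, so *m* < 8.33 mm.
- 5 to 6 mm is a 1.0 mm rise (20%). 6 to 8 mm is 2/6 = 33%. 8 to 9.6 mm is a 1.6 mm rise (20%).
- From 8.33 mm up to 10 mm, a 20% rise reaches 10 mm or more, so the overlap ends.

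CR also needs a non-pathologic nodal appearance, so size alone does not establish it.

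**Does another section settle it?**
- Table 9 (Section 6.1.3) maps target CR to overall CR and target PD to overall PD. It does not say which applies when one scan meets both.
- Section 8.3.3 exempts from PFS only residual disease found at surgical consolidation within 24 weeks of IMRT.
- Nothing removes nodes under 10 mm from the later sums.

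**Chance of a false call (assumptions stated).** Three post-treatment scans fall within a year of treatment start: 12–14 weeks after IMRT, then 6 and 9 months (about week 7 + 39 = 46). The 12-month scan falls at about week 7 + 52 = 59. Suppose true node sizes do not change, reading errors are independent and normal, and PD is a sum at or above 1.2 times the running minimum. The reading SD is assumed, because the documents give none. Simulated false PD:
- one 6 mm node: 1.4% at SD 0.3 mm, 15% at 0.5 mm, 46% at 1.0 mm
- one 8 mm node: 5% at 0.5 mm, 34% at 1.0 mm
- two 6 mm nodes: 0.04% at 0.3 mm, 4% at 0.5 mm, 31% at 1.0 mm
- three 8 mm nodes: 0.1% at 0.5 mm, 10% at 1.0 mm

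**Effect on the decision.** Section 9 states the PFS criterion in two ways. An observed rate of at least 60% is 24/40. A one-sided 90% exact lower bound above 0.60 needs 29/40 (bound 0.615; 28/40 gives 0.588). If a share *q* of truly progression-free patients is miscoded, the apparent rate is *p*(1 − *q*). With true *p* = 70%:

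| Assumed *q* | Apparent rate | P(at least 24/40) | P(at least 29/40) |
|---|---|---|---|
| 0 | 70% | 0.94 | 0.44 |
| 10% with such nodes × 15% miscoded = 1.5% | 0.70 × 0.985 = 69.0% | 0.92 | 0.38 |
| 30% with such nodes × 20% miscoded = 6% | 0.70 × 0.94 = 65.8% | 0.83 | 0.24 |

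At *q* = 5%, the chance of at least 29/40 falls from 0.715 to 0.510 for true *p* = 75%, and from 0.912 to 0.764 for true *p* = 80%.

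**The case against.** **Shrunken nodes may not count in the sum.** Section 6.1.2.1 builds the sum from pathologic target nodes, and a node under 10 mm is non-pathologic. On that reading a 6 mm node contributes nothing. But that wording defines the baseline sum. The PD rule refers simply to the target nodes, and no section drops them once they shrink. The objection shows ambiguity, not a rule that prevents the false call.

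**RECIST 1.1 may govern.** Section 8.3.1.1 and Appendix C call for assessment according to RECIST 1.1, and Section 6.2.4 credits RECIST 1.1 with the sub-centimetre node rule. Readers may therefore apply its progression text, which the documents do not reproduce. However, Sections 6 and 6.2.4 send the reader to Section 6.1 as a modified version, and that section writes out its own PD rule. The protocol does not say which prevails.

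**Recurrence after CR is treated as its own concept.** Section 6.1.3.4 ends a complete response at documented recurrence, with no percentage. That governs duration of response; it does not override the PD rule for PFS.

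**The size is unknown.** This stands in full. The documents give neither reading error nor the share of patients with residual nodes, and plausible inputs run from negligible to severe.

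**The rule is the same in both arms and errs conservatively.** This also stands. False progressions make the 60% bar harder to clear, so they cannot pass a poor schedule on that criterion.

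**Conclusion.** The gap is in the text: a patient who still meets CR can be scored as progressed on the same scan, and no other section resolves it. The overlap covers single-node (or equal-node) nadirs below 8.33 mm with the primary gone. The likely direction is a downward bias in 1-year PFS in both arms.

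Its size is conditional. For one stable 6 mm node, false PD runs from about 1% to 46% over assumed reading SDs of 0.3 to 1.0 mm; with several nodes and small error it is near zero.

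A reader might infer two stronger things. One is that 1-year PFS is invalidated by a known amount; the documents supply no measurement error or residual-node frequency to support that. The other is that the rule favours one schedule; the definition and the post-IMRT scan times are common to both arms, and nothing in the documents shows a difference. What remains is a defect in a decision endpoint that should be fixed, not one that by itself defeats the trial.

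**What to change.** Amend Section 6.1.2.1.3 in three parts.

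1. Require the 20% rise and a stated absolute rise in the sum. Take the value from the RECIST 1.1 text that the protocol names, or have the sponsor justify another. Section 6.2.1 is not a source for it: its 5 mm CT specification applies to chest, abdomen and pelvis, and it says head and neck tumours need specific procedures.
2. State that the target sum cannot trigger PD while the primary is absent and every target node remains under 10 mm in short axis with non-pathologic appearance, that is, while CR still holds.
3. State that this definition governs PFS.

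Part 2 must apply to the whole target set. A clause that only stops a single small node from causing PD by itself would miss five nodes each going from 5.0 to 6.2 mm: the sum goes from 25 to 31 mm, a rise of 6 mm or 24%. Nor is an absolute minimum enough alone. At an assumed SD of 1.0 mm, an illustrative 5 mm minimum cuts false PD for one 6 mm node from 46% to about 0.1%, but leaves five stable 6 mm nodes at about 11%, because 20% of any sum above 25 mm already exceeds 5 mm. Part 2 brings that case to about 0%. Part 1 still matters for nodes close to 10 mm, where noise can cross the limit.

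Leave the rules for new lesions and unequivocal non-target progression unchanged. The cost is a few sentences, with no new scans or patients. The downside is that a very small true regrowth may be dated one scan later.

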6.1.2.1.4 Stable Disease (SD)

Neither sufficient shrinkage to qualify for PR nor sufficient increase to qualify for PD.

6.1.2.2 Non-target Lesions

All other lesions or sites of disease. Measurements of these lesions are not required, but the presence or absence of each should be noted throughout follow-up.

6.1.2.2.1 Complete Response (CR)

The disappearance of all nontarget lesions and normalization of tumor marker levels, if applicable.

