6.1.2.2.2 Partial Response (PR)/Stable Disease (SD)

The persistence of one or more nontarget lesion(s).

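### Non-target complete response carries no size allowance for neck nodes, so the same normalised neck can be coded CR or PR (minor)

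*Combined protocol and SAP*

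**What the plan says.** Section 6.1.1.1.2 sorts neck nodes by short axis. Nodes of 15 mm or more are measurable. For the middle group it states: "Neck lymph nodes are considered pathologic but non-measurable if short axis ≥ 10 mm but < 15 mm". For the smallest: "Neck lymph nodes are considered non-pathologic and non-measurable if short axis < 10 mm".

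Section 6.1.2.1 sets the target lesions: "All measurable lesions, including the primary tumor, and up to a maximum of five neck lymph nodes, should be measured at baseline". Section 6.1.2.2 makes everything else non-target, requires no measurement of it, and asks only that presence or absence be noted.

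The CR rules then differ:

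- Target lesions (6.1.2.1.1): for radiographic CR in the neck, "the resolution of neck lymph nodes to < 10 mm in short axis diameter with non-pathologic appearance is sufficient".
- Non-target lesions (6.1.2.2.1): "The disappearance of all nontarget lesions and normalization of tumor marker levels, if applicable". Under 6.1.2.2.2, any non-target lesion that persists gives PR/SD.
- Table 9 (6.1.3): target CR with an incomplete non-target response is an overall PR.

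Section 6.2.4 explains why a nodal allowance is wanted: small, non-pathologic nodes can remain after chemoradiotherapy, and "for determination of CR, a short axis of < 1 cm is no longer considered residual disease". The modified RECIST 1.1 CR list at the end of that section has three conditions: the primary is gone; measurable pathologic nodes are under 10 mm, non-necrotic and of normal configuration; and there are no new pathologic lesions.

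**The concern.** The protocol moves away from RECIST 1.0 because requiring nodes to vanish is unsuitable after chemoradiotherapy. It then keeps that requirement, on its face, for the smaller pathologic nodes and for any measurable node beyond the fifth. The smaller nodes thus face a stricter test than the larger ones.

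What is at stake is the recorded response. Section 6 requires responses to be coded, Section 6.1.3 requires clinical and radiographic response to be recorded with primary and neck reported separately, and Section 8.3.1 makes RECIST 1.1 assessment mandatory. Duration of complete response (6.1.3.4) starts only once CR is met, so a patient coded PR for this reason contributes late or not at all. Duration of overall response (6.1.3.3) starts at CR or PR, whichever comes first, and is not shifted by the label.

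**Working it through.** The plan states no CR rate, no CR target and no frequency of 10 to under 15 mm nodes, so there is no figure to reproduce. The check is to run two patients through the rules.

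**Two patients with the same neck after treatment.** Both have a 35 mm primary that disappears and one pathologic neck node that ends at 8 mm with normal appearance. There are no new lesions.

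| Step | Patient A: node 16 mm at baseline | Patient B: node 12 mm at baseline |
|---|---|---|
| Node class (6.1.1.1.2) | measurable | pathologic, non-measurable |
| Lesion set (6.1.2.1, 6.1.2.2) | target | non-target |
| Target response (6.1.2.1.1) | CR: primary gone, 8 mm is under 10 mm | CR: primary gone |
| Non-target response (6.1.2.2.1, 6.1.2.2.2) | none to assess | node still visible, so PR/SD |
| Overall (Table 9), literal reading | CR | PR |
| CR list in 6.2.4 | CR | CR: no condition applies to this node |

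Patient B is PR by one operative definition and CR by another. A sixth measurable node fares the same way: it is non-target under 6.1.2.1 and must vanish under 6.1.2.2.1, whereas 6.2.4 asks only that a measurable node be under 10 mm and look normal.

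**The reverse gap in 6.2.4.** Because its list speaks only of measurable nodes, a 12 mm node that stays at 12 mm would not block CR there either. Section 6.2.4 as worded is therefore not a complete substitute for 6.1.2.2.

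**Size.** With 40 evaluable patients per arm (Section 9, Sample Size Determination), one reclassified patient moves a CR proportion by 1/40 = 2.5 percentage points.

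Beyond that, only an illustration is possible. Let f be the share of true complete responders who have a normalised but still visible non-target node. Both f and the true CR rate are assumptions; neither is in the documents. Coded CR = true CR × (1 − f):

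| Assumed true CR | f = 5% | f = 10% | f = 20% | f = 30% |
|---|---|---|---|---|
| 60% | 57% | 54% | 48% | 42% |
| 80% | 76% | 72% | 64% | 56% |

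For example, 0.60 × (1 − 0.20) = 0.48. The table shows the direction if the literal reading is applied throughout. It does not estimate the effect in this trial.

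**The case against.** The strongest reply is that the text does not compel PR. Section 6.1.2.1.1 words its nodal rule for the neck as a whole, although it is printed under target lesions. Section 6.1.1.1.2 calls any node under 10 mm non-pathologic, and Section 6.1.2.2 asks only whether each non-target lesion is present. An assessor could consistently record a normal-looking 8 mm node as absent and code CR. Neck response is also reported separately, and Section 6.2.2 brings endoscopy into the CR determination. This stands: PR is the literal reading, not the only one. It does not remove the problem, because two assessors can then code the same neck differently, and the short axis needed to apply a 10 mm rule need not have been recorded.

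The second reply is that nothing planned rests on CR. Section 9 accepts or rejects an arm on DLT, 1-year local failure and 1-year PFS, and otherwise plans Kaplan-Meier curves for overall and progression-free survival. The only secondary objective in Section 2.2 is toxicity. This also stands, and it is why the point is minor.

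A reader might go further and infer that the trial's CR rate is understated by a known and large amount, or that the choice between arms is distorted. The documents support neither. They plan no CR-rate analysis, they give no input from which a bias could be computed, and the trial is described as non-comparative. PFS (6.1.3.7) runs to progression or death, residual disease at consolidation surgery within 24 weeks of IMRT is not a progression event (8.3.3), and nothing ties local failure or DLT to the CR/PR label. Nor does the protocol accept every node under 10 mm: it also requires a non-pathologic appearance (6.1.2.1.1), or a non-necrotic one with normal configuration (6.2.4).

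**Conclusion.** The inconsistency is real on a literal reading. Sections 6.1.2.2.1 and 6.1.2.2.2 with Table 9 require non-target neck nodes to disappear, Section 6.1.2.1.1 and the rationale in 6.2.4 accept normal-looking nodes under 10 mm, and the CR list in 6.2.4 has no separate non-target condition. The coded response and the duration of CR can therefore depend on baseline node size or on the assessor's reading.

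Under-calling of CR is the likely direction, assuming the non-target rule and Table 9 are applied as written. Its size cannot be determined from the documents; the 2.5 points per patient is the only figure that follows from the plan itself. The three primary metrics as defined, the acceptance criteria and the 90 patients to be randomised are unaffected. Severity: minor.

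**What to change.** Four wording changes, made together so that no new contradiction is left behind:

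1. Section 6.1.2.2.1: define non-target CR as disappearance of every non-nodal non-target lesion, with every non-target neck node under 10 mm in short axis and of non-pathologic appearance. Leave the tumor-marker clause as it is.
2. Section 6.1.2.2.2: for neck nodes, define persistence as a short axis of 10 mm or more, or a pathologic appearance.
3. Section 6.1.2.2: require the short axis of non-target neck nodes to be recorded, in place of the statement that no measurement is needed.
4. Section 6.2.4, CR list: drop the restriction to measurable nodes, so that the criterion covers all pathologic neck nodes.

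The cost is a few lines of text and slightly more recording from the same CT; no new scan is needed. The rule is best settled before responses are coded. The trial is open-label, and sizes not recorded at the time might have to be re-read from the images.
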